3.1.2 Part 2: Combination Dose Finding

This part will only be initiated following approval of a substantial amendment supporting the ANV419 starting dose in the combination part. The submission will include data from ANV419-001 Study and from Part 1 of this trial, and occurat any time when at least 2 responses have been observed in the Monotherapy Dose Expansion part.

The Combination Dose Finding part will be comprised of 2 arms (Arms B and C) that will identify a recommended Phase 2 dose (RP2D) for ANV419 in each arm when administered in combination with pembrolizumab (Arm B) or ipilimumab (Arm C) at the prescribed dosing. The number of patients recruited to each arm will be between 6 and 25 patients depending on the number of dose increments possible. A minimum of 6 patients will be treated at RP2D. The patients from the Combination Dose Finding part will not be randomized into the Combination Dose Expansion part.

[figure not shown]

Table 5. ANV419 Dose Escalation Plan for Combination Dose Finding Part (Pembrolizumab or Ipilimumab)

Dose Level	ANV419 Dose	Pembrolizumab Dose or Ipilimumab Dose	Frequency		
1					
2					
3					
4					
5					
Note: ANV419 will be administered by IV infusion over 15 minutes (+5 minutes).					
1. Dose increments will be determined by the SRC based on a synthesis of all relevant data available from all dose levels evaluated in this study, not exceeding a 3-fold increment from one dose level to the next. The maximum dose level explored will not exceed the dose of ANV419 monotherapy studied in the ongoing ANV419-001 study.					

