3 STUDY DESCRIPTION

3.1 Summary of Study Design

This is a multi-site, open-label, randomized, parallel arm, Phase 1/2 adaptive study to evaluate the efficacy and safety of ANV419 as a monotherapy and in combination with pembrolizumab or ipilimumab in patients aged 18 years or older with advanced CM who have previously been treated with at least 1 line of standard of care immunotherapy, including an anti-PD-1/anti-PD-L1 antibody.

The 4 following treatment arms will be included in this study:

- Arm A1:
- Arm A2:
- Arm B: in combination with pembrolizumab (Keytruda®); and
- Arm C: in combination with ipilimumab (Yervoy®).

There will be up to 3 separate parts in this study: Part 1: Monotherapy Dose Expansion with patients randomized to receive infusion of ANV419 (

If Part 1 is successful, Part 2: Combination Dose Finding with patients randomized to Arms B and C with infusion of ANV419 and finally, Part 3: Combination Dose Expansion with patients randomized to Arms B and C (see Figure 3). A total of up to 130 patients are planned to be enrolled in the study: a maximum of 30 patients in the Monotherapy Dose Expansion part, a maximum of 50 patients in the Combination Dose Finding part, and a maximum of 50 patients in the Combination Dose Expansion part and Combination Dose Expansion part will be stratified by BRAF mutation status.

In the Combination Dose Expansion part, the number of patients within each arm will be determined by pre-defined decision rules presented in Table 5.

[figure not shown]

Figure 3. Study Design

In the Combination Dose Finding part, patients will be manually randomized to Arm B or Arm C. In the Monotherapy Dose Expansion part and the Combination Dose Expansion part, patients will be randomized by IRT into Arms A1 or A2 and Arms B or C, respectively.

^{* =} If ANV419 monotherapy is successful, the combination portion will be initiated.

^{** =} Dose escalation increment is decided by the SRC until RP2D of ANV419 per arm is identified.

^{*** =} Arm not meeting pre-specified ORR criteria may be stopped early after Stage 1.

Ipi = ipilimumab; IRT = Interactive Response Technology; ORR = objective response rate; Pembro = pembrolizumab; R = randomization; RP2D = recommended Phase 2 dose; SRC = Safety Review Committee.

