4.1 Inclusion Criteria

Patients who meet all of the following criteria will be eligible to participate in the study:

- 1. Must provide written informed consent for the study;
- 2. Must be able to comply with the Protocol as judged by the Investigator;
- 3. Are \geq 18 years of age on day of signing informed consent;
- 4. Have histologically confirmed Stage 3 (unresectable) or Stage 4 (metastatic) CM, as per the American Joint Committee on Cancer staging system, eighth edition;
- 5. Have documented radiological progression on prior systemic therapy;
- 6. Have previously received anti-PD-1/L1 as monotherapy or in combination. A maximum of 2 prior lines of systemic therapy is allowed for BRAF wild-type disease and a maximum of 3 prior lines of systemic therapy is allowed for BRAFV600 positive disease;

Note: Adjuvant treatment is considered as a line of therapy only if patient experienced relapse/progression on therapy or within 6 months from adjuvant therapy completion;

- 7. Have measurable disease based on RECIST;
- 8. Have a performance status of 0 or 1 on the ECOG Performance Status;
- 9. Have adequate organ functions as defined in Table 9:

Table 9. Adequate Organ Function Laboratory Values

System	Laboratory Value
Hematological	
ANC	≥1500/μL
Platelets	≥100,000/μL
Hemoglobin	≥9 g/dL or ≥4.96 mmol/L
Renal	
Measured or calculated ¹ CrCl (GFR can also	
be used in place of CrCl)	≥30 mL/min
Hepatic	
	\leq 1.5 × ULN OR \leq 1.5 × ULN for patients with total bilirubin
	levels >1.5 × ULN; direct bilirubin \leq 1.5 × ULN for patients with
Serum total bilirubin OR direct bilirubin	Gilbert's syndrome
AST (SGOT) or ALT (SGPT)	$\leq 2.5 \times \text{ULN } \underline{\text{OR}} \leq 5 \times \text{ULN for patients with liver metastases}$
Albumin	>2.5 g/dL

^{1.} CrCl should be calculated per Cockcroft-Gault equation.

ALT = alanine aminotransferase; ANC = absolute neutrophil count; AST = aspartate aminotransferase; CrCl = creatinine clearance; GFR = glomerular filtration rate; SGOT = serum glutamic oxalacetic transaminase; SGPT = serum glutamic pyruvic transaminase; ULN = upper limit of normal.

- 10. Female patients of childbearing potential must have a negative serum pregnancy test at the Screening Visit and a negative (urine or serum) pregnancy test within 72 hours prior to study Day 1. If the urine test is positive or cannot be confirmed as negative, a serum pregnancy test will be required and must be negative for the patient to be eligible;

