4.2 Exclusion Criteria

Patients who meet any of the following criteria will be excluded from participation in the study:

- 1. Have received investigational agent (including investigational device) within 4 weeks or an interval of 5 half-lives of the respective investigational agent prior to study Day 1, whichever is longer, with the exclusion of an anti-PD-1/anti-PD-L1 antibody given as either a single agent or non-CTLA-4 antibody containing combination (eg, anti-lymphocyte-activation gene 3 antibody);
- 2. Have a known hypersensitivity to ANV419 or to any of the excipients, such as sucrose, histidine or polysorbate 80. For combination arms only: Have hypersensitivity to pembrolizumab or ipilimumab or any of their excipients;
- 3. For combination arms only: Have previously discontinued ipilimumab, pembrolizumab, or any other PD-1/PD-L1 inhibitors due to unacceptable drug-related toxicity (defined as toxicities that required second line immunosuppression, ie, not controlled by steroids alone);
- 4. Have an LDH level of $\geq 2 \times$ upper limit of normal;
- 5. Have not recovered (ie, ≤Grade 1 or at baseline with the exception of alopecia or fatigue [up to Grade 2 allowed]) from AEs resulting from prior immunotherapies. Patients who have autoimmune AEs controlled by replacement therapy (ie, hypothyroidism) due to previous treatment are eligible provided replacement therapy has been initiated and toxicity has returned to Grade 1;
- 6. Have not recovered (ie, ≤Grade 1 or at baseline) from toxicities due to a previously administered prior chemotherapy, targeted small molecule therapy, or radiation therapy;
 - Note: If the patient received major surgery, they must have recovered adequately from the toxicity and/or complications from the intervention prior to starting study drug. Major surgery is defined as any surgery requiring entrance into a body cavity (eg, chest, abdomen, or brain), organ removal, normal anatomy alteration, or joint replacement. Minor surgery is defined as any surgery in which skin, mucosa, or connective tissue sections are altered (eg, biopsy, cataract, endoscopic procedures, etc).
- 7. Have been diagnosed with uveal/ocular or mucosal melanoma;

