- 17. Have a history or current evidence of any condition, therapy, or laboratory abnormality that might confound the results of the study, interfere with the patient's participation for the full duration of the study, or it is not in the best interest of the patient to participate, in the opinion of the treating Investigator;
- 18. Have known psychiatric or substance abuse disorders that would interfere with cooperation with the requirements of the study;
- 19. Are pregnant or breastfeeding, or expecting to conceive or father children within the projected duration of the study, starting with the Screening Visit through 6 months after the last dose of study drug;
- 20. Are known to be human immunodeficiency virus (HIV) positive (or tests positive for HIV 1 or 2 at Screening), unless the following criteria are met:
 - a. CD4+ lymphocyte count >350 μ L;

- b. Had no history of acquired immunodeficiency syndrome (AIDS)-defining opportunistic infections within the past 12 months;
- c. Have been on established anti-retroviral therapy for at least 4 weeks; and
- d. Have an HIV viral load of <400 copies/mL prior to study Day 1.

Note: Patients on strong cytochrome P450 (CYP)3A4 inhibitors or strong CYP3A4 inducers must be switched to an alternate effective anti-retroviral therapy regimen prior to study treatment or are excluded if regimen prior to study Day 1 cannot be altered.

21. Have uncontrolled hepatitis B infection or hepatitis C infection;

Note: Patients with hepatitis B (positive hepatitis B surface antigen) who have controlled infection (serum hepatitis B virus DNA by polymerase chain reaction that is below the limit of detection and receiving anti-viral therapy for hepatitis B) are permitted. Patients with controlled infections must undergo periodic monitoring of hepatitis B virus DNA.

Note: Patients with hepatitis C (positive hepatitis C virus antibody) who have controlled infection (undetectable hepatitis C virus RNA by polymerase chain reaction either spontaneously or in response to a successful prior course of anti-hepatitis C virus therapy) are permitted.

22. Have received a live vaccine within 30 days of study Day 1; or

Note: Seasonal influenza vaccines for injection are generally inactivated flu vaccines and are allowed; however, intranasal influenza vaccines (eg, Flu-Mist®) are live attenuated vaccines, and are not allowed.

23. For combination arms only: Have received solid organ or hematopoietic stem cell transplant.

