6.11 Immunogenicity Analyses

Blood samples for anti-drug antibodies (ADA) will be drawn as indicated in Appendix A and analyzed at a central laboratory. Please refer to the laboratory manual for details. Additional samples will be taken in the case of an IRR or irAE to rule out involvement of ADA. ADA samples will be analyzed for anti-ANV419 antibodies, their cross-reactivity to human IL-2, and their capacity to neutralize ANV419 function in a cell-based assay. In case of a Grade 3 or higher IRR, irAE, or any other AE deemed clinically suspicious of an irAE as judged relevant by the SRC, all available ADA samples from the respective patient will be analyzed immediately.

The probability of inducing a clinically relevant anti-ANV419 immune response is considered to be moderate. The most important potential risk associated with an anti-ANV419 humoral immune response is neutralization of endogenous IL-2, as this might result in systemic activation of immune effector cells. However, no such response was observed to aldesleukin, and therefore, this risk for severe consequences is considered low. In conclusion, the overall immunogenicity risk in the context of oncology indications is considered low to moderate as the probability of an ADA response is moderate while the severity of possible consequences is considered to be low.

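### No eligibility criterion excludes prior ANV419, and only transfer from Part 2 to Part 3 is barred, so the Part 3 ORR could be diluted by patients who have already failed the drug

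*Protocol*

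**What the plan says.** Protocol section 3.1.2, repeated in the synopsis and in SAP section 2.2.1.2, separates the two combination parts: "The patients from the Combination Dose Finding part will not be randomized into the Combination Dose Expansion part". There is no matching sentence for movement from Part 1 to Part 2, from Part 1 to Part 3, or from ANV419-001 into this study.

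The criteria that bear on prior ANV419 are these:

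- Exclusion 1 (section 4.2) is a time-limited washout: "Have received investigational agent (including investigational device) within 4 weeks or an interval of 5 half-lives of the respective investigational agent", whichever is longer.
- Exclusion 2 is the only criterion that names ANV419, and it concerns allergy: "Have a known hypersensitivity to ANV419 or to any of the excipients".
- Exclusion 17 could be used case by case: "Have a history or current evidence of any condition, therapy, or laboratory abnormality that might confound the results of the study". It applies in the opinion of the treating investigator and does not mention ANV419.
- Inclusion 6 (section 4.1) limits previous treatment: "A maximum of 2 prior lines of systemic therapy is allowed for BRAF wild-type disease and a maximum of 3 prior lines" for BRAFV600 disease.
- Inclusion 5 requires radiological progression on earlier systemic therapy. Progression on ANV419 in Part 1 could itself meet this.

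Section 3.1 sets the size of the Part 1 pool: "a maximum of 30 patients in the Monotherapy Dose Expansion part". Section 3.1.2 lets the Part 2 submission go in once at least 2 responses have been seen in Part 1. It also requires a substantial amendment, described as supporting the starting dose; eligibility is not mentioned.

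**The concern.** The sponsor saw the need to keep the expansion cohort separate from the dose-finding cohort, but wrote the rule for one route only. Patients who progressed on ANV419 alone would already be known to the sites when a combination containing the same drug opens.

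Part 3 judges each arm against ORRs of 20% and 40%. If part of an arm has already failed ANV419 and responds less often, the arm's ORR mixes two populations. An active combination could then be stopped after 12 patients or miss its final threshold, and the estimate would not describe ANV419-naive patients.

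A second, weaker worry concerns Part 2. Section 6.11 states: "The probability of inducing a clinically relevant anti-ANV419 immune response is considered to be moderate". Antibodies carried over from earlier dosing could distort exposure and DLT data in a part with at most 25 patients per arm.

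**Working it through.** **1. Who can re-enter.** Assume that ANV419 received in Part 1 counts as one line; the protocol does not say. A BRAF wild-type patient with 1 line before Part 1 then has 2 and is still eligible; one with 2 lines then has 3 and is not. A BRAFV600 patient with 1 or 2 lines then has 2 or 3 and is still eligible. Performance status, LDH, and recovery from earlier toxicity must also be satisfied. From ANV419-001, section 1.3.4 reports 34 treated patients with mixed tumour types and several previous lines. Only those with cutaneous melanoma within the cap could qualify, and their number is not given. The route is open, but for a subset only.

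**2. Reproducing the plan's design.** Inputs from Protocol section 8.2.1: null ORR 20%, alternative 40%, type I error at most 10%, power at least 80%, 12 + 13 = 25 patients per arm. Section 8.2.3 stops an arm at 2 or fewer responses of 12. No final count is stated. A search over two-stage designs gives Simon's optimal design as 2/12 and 7/25: continue at 3 or more of 12, succeed at 8 or more of 25. This matches the stated sample sizes.

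Probability of success = sum over x1 = 3 to 12 of P(X1 = x1) × P(X2 ≥ 8 − x1), with X1 ~ Bin(12, p) and X2 ~ Bin(13, p).

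- p = 0.20: 0.099, within the 10% limit.
- p = 0.40: 0.815, above the 80% requirement.

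Wrongful Stage 1 stopping at p = 0.40 is P(X1 ≤ 2) = 0.6^12 + 12 × 0.4 × 0.6^11 + 66 × 0.4² × 0.6^10 = 0.0022 + 0.0174 + 0.0639 = 0.083.

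**3. Dilution.** The documents give neither the share f of previously exposed patients nor their ORR q. Both are assumed here: f of 10-20% and q of 10-20%, with 40% in everyone else. Then p = (1 − f) × 0.40 + f × q.

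| f | q | Arm ORR p | Power (≥3/12, ≥8/25) | Stopped at Stage 1 |
|---|---|---|---|---|
| 0 | – | 0.40 | 0.815 | 0.083 |
| 10% | 20% | 0.36 + 0.02 = 0.38 | 0.759 | 0.107 |
| 10% | 10% | 0.36 + 0.01 = 0.37 | 0.728 | 0.120 |
| 20% | 20% | 0.32 + 0.04 = 0.36 | 0.694 | 0.135 |
| 20% | 10% | 0.32 + 0.02 = 0.34 | 0.620 | 0.169 |

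Even the mildest row is below the required 80%. If q were 40%, nothing would be lost.

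**4. Is the assumed share possible?** 10-20% of 25 is 2.5 to 5 patients per arm, so 5 to 10 over two full arms, against a Part 1 pool of at most 30. That is feasible in number. Nothing in the documents says how likely it is.

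**The case against.** **Re-entry is not what the plan describes.** The enrolment ceiling of 130 equals 30 + 50 + 50, which fits each patient being counted once. Section 4.4 sends patients who discontinue treatment to follow-up, and no crossover or re-screening procedure is given. This stands as evidence of intent. It is not a prohibition, and the one explicit bar in section 3.1.2 covers a different route.

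**The pool is small.** The line cap, tumour type, recovery criteria and exclusion 17 all narrow it. A Part 1 patient treated elsewhere while Part 2 runs would use a further line. All of this stands, and it is why the number of re-entrants is left unknown. A reader might infer that Part 1 patients are likely candidates, or that the hypersensitivity wording in exclusion 2 presupposes exposed patients. The text supports neither.

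**The power figure rests on an inferred rule.** This also stands. The written final rule in section 8.2.4 asks for a 95% confidence interval with its lower limit above 20%. By Clopper-Pearson that needs 10 of 25, with power 56.9% before any dilution and 32.5-48.7% over the same four scenarios. The loss appears under either rule.

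**The dose-finding consequence.** A reader might go further and infer that carried-over antibodies lower the DLT rate, so that the recommended dose is set too high. The documents do not support that:

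- Section 6.11 names neutralised endogenous IL-2, with systemic immune activation, as the most important potential risk. That could mean more toxicity.
- SAP section 3.7 leaves the direction of any antibody effect open.
- DLTs are assessed with pembrolizumab or ipilimumab, which carry toxicity of their own, so previously exposed patients cannot be given a DLT risk of zero.
- The BOIN boundaries are blacked out. Under the default boundaries for a 25% target (0.197 and 0.298), 0/3 and 1/6 escalate while 1/3 and 2/6 de-escalate. No result at 3 or 6 patients means staying at the dose, so comparing an average DLT rate with a boundary says little about actual decisions.

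**Conclusion.** The eligibility gap is real. As written, the plan lets a patient who has already failed ANV419 into the Part 3 response test, provided the line cap is met and no investigator applies exclusion 17. If 10-20% of an arm were such patients with an ORR of 10-20%, the arm's ORR would be 34-38%. Power of the inferred Simon design would fall from 81.5% to 62-76%, and wrongful Stage 1 stopping would rise from 8% to 11-17%. The share and its response rate are assumptions, and no statement in the documents fixes either.

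For Part 2, the most that can be said is that carried-over antibodies could distort exposure and DLT data in an unknown direction and by an unknown amount. No claim is made that they would lower the DLT rate.

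SAP sections 1 and 5 record that the trial stopped after Part 1 with no responses, so no data from Parts 2 or 3 are affected. The same gap would have allowed an ANV419-001 patient into Part 1; the documents do not show whether any entered. This is a cheap improvement to the design rather than a flaw in a reported result.

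**What to change.** Add one exclusion to Protocol section 4.2 and the synopsis: previous treatment with ANV419 in any study or in any part of this study. Extend the sentence in section 3.1.2, with its copies in the synopsis and SAP section 2.2.1.2, to say that Part 1 patients do not enter Parts 2 or 3.

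The cost is two short edits, which could go into the substantial amendment that Part 2 already requires. The downside is that a few otherwise eligible patients could not re-enter.

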3.1.2.1 Bayesian optimal interval dose escalation guidelines

In the Combination Dose Finding part, dose escalation will follow the Bayesian optimal interval (BOIN)²⁹ design with the following predefined rules to find the MTDs/RP2Ds of ANV419 in combination with pembrolizumab or ipilimumab to be used in the efficacy analysis:

SRC = Safety Review Committee; TBD = to be determined.

- Target DLT rate of 25%;
- Maximum of 25 patients;
- Maximum of 9 patients treated at the same dose level; and
- Maximum of 5 dose levels defined in Table 5 to be tested.

[figure not shown]
As shown in Figure 4, the BOIN²⁹ design uses the following rules, optimized to minimize the probability of incorrect dose assignment, to guide dose escalation/de-escalation:

- If the observed DLT rate at the current dose is ≤ _____, escalate the dose to the next higher dose level:
- If the observed DLT rate at the current dose is > _____, de-escalate the dose to the next lower dose level; and
- Otherwise, stay at the current dose.

The steps to implement the BOIN design are described as follows:

- 1. Patients in the first cohort with a cohort size of 3 patients are treated at dose level 1;
- 2. To assign a dose to the next cohort of patients, conduct dose escalation/de-escalation according to the rule displayed in Table 6; and
 - Note: If none of the actions (ie, escalation or de-escalation) is triggered, treat the new patients at the current dose.
- 3. Repeat step 2 until the maximum sample size of 25 is reached or a stopping rule is met, or if the number of evaluable patients treated at the current dose reaches 9 and the decision according to Table 6 is to stay at the current dose.

After the study is completed, the MTD will be selected based on isotonic regression as specified by Liu and Yuan.²⁹ Specifically, the MTD will be selected as the dose for which the isotonic estimate of the toxicity rate is closest to the target toxicity rate. If there are ties, select the higher dose level when the isotonic estimate is lower than the target toxicity rate and select the lower dose level when the isotonic estimate is greater than or equal to the target toxicity rate.

[figure not shown]
[figure not shown]

Figure 4. Flowchart for Trial Conduct Using the BOIN Design

BOIN = Bayesian optimal interval; DLT = dose-limiting toxicity; MTD = maximum tolerated dose.

Operation characteristics

Table 7 shows the operating characteristics of the trial design and based on 1000 simulations of the trial using R package "BOIN" (BOIN v2.7.0.0).³⁰ The operating characteristics show that the design selects the true MTD, if any, with high probability and allocates more patients to the dose levels with DLT rate closest to the target of

